## Study Design and Methods

Subjects will be recruited and randomized into two groups using a random block method at the end of the baseline visit. One group will receive the FES intervention and the other group will continue with their activities of daily living. The study consists of a baseline visit and four follow up visits at 4 weeks, 8 weeks, 12 weeks and one final visit three months from the 12 week visit or from the discontinuation of the FES. Outcome measures will be taken for both groups during these visits. Each visit is expected to take no more than two hours.

Following informed consent, it will be verified and documented that participants meet the inclusion/exclusion criteria. Most of the inclusion/exclusion criteria are self report, with the exception of the monofilament evaluation and the evaluation of voluntary muscle contraction. An investigator will administer the tests. For the sensory testing the participant will be asked to close their eyes and inform the investigator when they sense the pressure of the monofilament on their LE. In order to continue with the study procedures, the participant must be able to feel a minimum of 7 of the 10 areas tested. Participants will also be evaluated to determine if a voluntary muscle contraction is present. To do this the FES electrode pads will be placed on the participant and the investigator must be able to observe a muscle contraction in order to proceed. Any participants who do not meet the inclusion/exclusion criteria for the study will be withdrawn.

The following procedures and outcome measures will be obtained from a blinded (second) assessor at the baseline visit.

1. Residual knee extension strength will be tested using a standardized Biodex protocol and a custom attachment (System 3, Biodex Medical Systems, NY). The participant will practice first on the biodex machine with their intact limb.

2. The residual limb volume will be measured with the use of a hand held three-dimensional motion-tracking laser scanner system. Reflective markers will be placed on a sock over the residual limb located at the tibial tubercle, fibular head, and anterior distal tibia. Circumferential measurements of the residual limb will be taken with a tape measure. Longitudinal measurements of the residual limb will be taken with a straight ruler. Using a standard scale, participant's height and weight will be recorded.

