follow: lag delay of 3 seconds, ramp up time of 2 seconds, on time of 9 seconds and ramp down of 1 second. For the smaller muscles of the gastroc/soleus and anterior tibialis muscles we will start with the setting of the 300ms pulse width and 35 Hz for the pulse rate. There will be no lag delay. Channel 1 settings will be as follows: ramp up time of 2 seconds, on time of 10 seconds and ramp down time of 2 seconds. Channel 2 settings will be as follows: ramp up time of 2 seconds, time on of 10 seconds and a ramp down for 2 seconds. The pulse rate and width will be increased at each visit per participant's comfort level.

We will record the settings at each visit and instruct the patient to not change the settings. The Continuum device locks the intensity increase buttons to prevent accidental increases in intensity. This safety feature is activated after 20 seconds of unchanged intensity.

Both study groups will be given daily logs to record daily prosthetic wearing times, changes in health, medications, activity, pain levels and FES use (the intervention group only).

Intervention group participants will be directed to use the FES for 15 contractions per muscle group (totally approximately 45 minutes) a minimum of three times per week for the next three months at home. We will set up a face-to-face visit with the FES participants at the end of the first week and call the FES participants every two weeks thereafter to check on compliance and address any issues with using the device. If the participant reports an ill-fitting prosthesis during the study, we will refer the participant to their local prosthetist for proper adjustments. If the prosthetic socket warrants replacement, the participant will be withdrawn from the FES intervention, we will perform the above mentioned outcome measures and continue to follow them until the 3 month final follow up visit.

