At each follow up visit the log book entries will be collected and reviewed. A second investigator will inspect the residual limb and check the fit of the prosthetic socket, record residual limb knee extension strength on the Biodex machine, take anthropometric measurements (circumferences and lengths) of the residual limb with a tape measure and ruler, and scan the limb with the hand held three-dimensional motion-tracking laser scanner system. The participant will be asked to complete the pain questionnaire at all four followup visits and the Prosthetic Evaluation Questionnaire (PEQ) at the 12 weeks and 3 month followup visits.

For the isokinetic evaluation with the Biodex, the individuals will be positioned in the dynamometer, sitting with the trunk, pelvis and thigh stabilized by belts. The back of the chair will be inclined at an 85 degree angle and the rotational axis of the device will be aligned with the rotational axis of the knee joint, at the level of the lateral epicondyle of the femur. The lever arm was positioned parallel to the leg, with the support cushion modified for the amputee and positioned at the mid-calf. The test will be performed in a total range of motion of 110 degrees. The knees will be positioned in 60 degrees of flexion to start.

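### Socket fit is checked only after randomisation, so a participant whose socket already needs replacing can be allocated to FES and then taken off it

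*Combined protocol and SAP*

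**What the plan says.** All of the following is in the Combined protocol and SAP, Study Design and Methods, unless stated otherwise.

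- **Timing of allocation.** "Subjects will be recruited and randomized into two groups using a random block method at the end of the baseline visit".
- **Screening.** "Most of the inclusion/exclusion criteria are self report, with the exception of the monofilament evaluation and the evaluation of voluntary muscle contraction". The Eligibility Criteria cover residual limb length, time since surgery, pain, prior stimulation, contraction, cardiac status, sensation and BMI. None concerns the socket or the fit of the prosthesis.
- **Baseline measures.** "The following procedures and outcome measures will be obtained from a blinded (second) assessor at the baseline visit". Five items follow: knee extension strength; limb volume and dimensions with height and weight; a pain questionnaire; the PEQ; and gait.
- **Socket check.** In the paragraph on follow-up visits: "A second investigator will inspect the residual limb and check the fit of the prosthetic socket". This is the only place where the check appears.
- **Poor fit.** "If the participant reports an ill-fitting prosthesis during the study, we will refer the participant to their local prosthetist for proper adjustments".
- **Replacement.** "If the prosthetic socket warrants replacement, the participant will be withdrawn from the FES intervention". For these people, "we will perform the above mentioned outcome measures and continue to follow them until the 3 month final follow up visit".

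**The concern.** A condition that ends the intervention should be looked for before the intervention is allocated. Here the plan names such a condition, has a check that bears on it, and schedules that check only after allocation. The stopping rule makes no exception for a socket that was already failing at entry.

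Two things are at stake. First, an affected FES participant receives less than the planned dose, which weakens the contrast between arms when they are compared as allocated. A replacement socket during follow-up may also change PEQ scores and gait (Hypothesis 4) independently of FES. Strength and volume (Hypotheses 1 and 2) are measured on the limb, so that second route is less direct for them.

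Second, without a baseline rating of fit, a misfit found later cannot be classed directly as present at entry or new since FES began. This matters because Hypothesis 2 expects limb volume to increase and the Background reports clinical experience of better socket fit with FES. The baseline scan, tape measurements and PEQ give only an indirect reference.

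**Working it through.** The plan states no figure on this point: it gives no rate of poor fit at entry and none of withdrawal from FES. The check is a reading of the visit sequence, followed by simple arithmetic on dose.

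**Sequence**

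1. Consent, then eligibility. The investigator's tests are the monofilament test and observation of a contraction. The socket is not among them.
2. Five baseline measures. None rates fit, and no rule links any of them to eligibility on socket grounds.
3. Randomisation.
4. FES participants only: a face-to-face visit at the end of week 1, then calls every two weeks. Their stated purpose is compliance and problems with the device, but a participant could report a poor fit at any of them.
5. Week 4: the first scheduled socket check.
6. If the participant reports poor fit: referral. If replacement is warranted: FES stops and follow-up continues.

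Nothing in steps 1 to 3, as written, would hold back someone whose socket already needs replacing.

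**Exposure lost per affected FES participant**

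Inputs: the dose is "15 contractions per muscle group (totally approximately 45 minutes) a minimum of three times per week for the next three months at home", and the device is returned at the 12-week visit. I take three months as 12 weeks and assume use at exactly the minimum frequency until the stop.

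- Planned minimum: 12 weeks × 3 per week = 36 sessions.
- Delivered by a stop at the end of week *w*: 3*w*. Lost: 36 − 3*w*. Share lost: (36 − 3*w*)/36.

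| FES stops at end of week | Delivered | Lost | Share lost |
|---|---|---|---|
| 1 | 3 | 33 | 92% |
| 4 | 12 | 24 | 67% |
| 6 | 18 | 18 | 50% |
| 8 | 24 | 12 | 33% |
| 12 | 36 | 0 | 0% |

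Week 1 is the first scheduled contact after allocation, and week 4 is the first socket check. Weeks 6 and 8 would be the stop dates if FES continued through an assumed 2 or 4 weeks of referral after a week-4 finding. The documents do not say whether FES pauses during referral.

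**Arm level**

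The arm-level loss is the share of FES participants affected multiplied by the loss per person. The documents do not give the first factor, which could be zero, so the product is not computed.

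**The case against.** The strongest case against runs as follows.

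- **The lists may not be complete.** The follow-up paragraph omits the gait test, although Hypothesis 4 needs gait after training. Absence from the baseline list is therefore weak evidence that nobody looks. Before allocation, pads are placed on the limb, the limb is scanned and measured, the participant walks on the gait system, and the PEQ asks about the prosthesis. This stands in part: an obviously failing socket may well be noticed. But no rule says what to do about it, and the investigator with a CPO credential is named only for fitting the device after allocation.
- **Problems may surface before week 4.** The referral step starts from a participant's report, which could come at the week-1 visit or in a call. This stands, and it is why week 4 is not used as the only stopping point. It does not weaken the point, because such reports still come after allocation and an earlier stop loses more.
- **The harm has no direction.** Socket status at entry precedes randomisation and is balanced in expectation. This stands. A reader might infer a biased comparison or missing outcomes. The documents support neither: those withdrawn from FES are still measured and followed. The extra contacts in the FES arm could prompt more reports there, but nothing says they ask about the socket, so no direction is claimed.
- **The baseline assessor may not be able to judge replacement.** This stands. The documents state no qualification for that judgement and no criterion, so the decision should go to the prosthetist, as it can under the existing referral step.

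**Conclusion.** The point holds as a cheap improvement to the design. Followed as written, the plan can allocate to FES a person who already meets its own condition for stopping FES. The consequence is avoidable loss of exposure and a possible new-socket effect on PEQ and gait, in an unknown number of people.

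Per affected person, the loss is about 92% of the minimum sessions for a week-1 stop, 67% for a week-4 stop, and less for later stops. This assumes use at the minimum frequency and a 12-week course.

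Three stronger readings go beyond the documents:

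- **A percentage loss for the whole arm.** This would need a prevalence that the documents do not give.
- **Withdrawal triggered by the follow-up socket check itself.** The plan does not say so. It describes referral after a participant's report, and then withdrawal if replacement is warranted.
- **The planned compliance covariate resolves the matter.** Hours of FES use in the Statistical Plan may describe lower exposure, but cannot restore it.

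How that covariate is averaged after an early stop, and when the final visit then falls, are separate questions that arise for any early stop. A baseline socket check settles neither.

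**What to change.** In Study Design and Methods, add the limb inspection and socket-fit check to the baseline visit, before randomisation, and record the result as the reference for later checks. If fit is poor, refer the person to the local prosthetist before randomising:

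- If the prosthetist judges that only adjustment is needed, the person stays eligible.
- If the prosthetist judges that replacement is warranted, defer the person and re-screen after refitting.

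Add one line to the Eligibility Criteria to match. Socket problems that arise after entry stay under the existing rule.

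The cost is a short amendment and a few minutes at a visit already held, for a check already planned at four later visits. Recruitment will be slightly slower where a referral is needed. The entry population will be slightly narrower, limited to the exclusion of people whom the plan would take off FES if they were allocated to it. The change does nothing for sockets that come to need replacing during the trial, including any affected by a change in limb volume under FES.

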Most studies on FES have shown positive results when combining FES with activity (e.g. knee flexion/extension exercises, cycling etc.) (9). It is difficult to exercise a muscle that has been amputated and is partially intact. FES conditions the muscle similar to exercise. Our clinical experience has found improvements in knee function, socket fit, and reductions in pain with wearing FES alone. With this study, one of the main functional outcomes that we are investigating is knee extension. We plan to place the FES electrodes on the medial and lateral quadriceps muscles in hope to show positive changes in muscle strength and volume. The gastroc/ soleus and tibialis anterior muscles have been amputated and have a secondary insertion point, therefore they are difficult to strengthen by exercising. We would like to investigate the effects of the FES on these two muscles in hopes to decrease atrophy or increase muscle volume. Should we demonstrate that FES alone helps improve the outcome measures in this study; it could potentially be a highly practical, easy to use, cost effective treatment that can be done at home.

**Objective:** To determine if at-home FES use without prosthetic wear results in benefits to persons with unilateral, trans-tibial amputations (TTA) who are at least two years status post their amputation surgery.

Hypothesis 1: FES will increase knee extension strength in the residual limb

Hypothesis 2: FES will increase volume of the residual limb

Hypothesis 3: FES will decrease chronic and phantom pain of the residual limb

Hypothesis 4: In comparison to the control group, FES training will show greater increases in velocity, step length, and percentage in stance time on the amputated limb after training when compared to baseline as measured using the GaitRite System.

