Muscle performance will be evaluated at angular velocity of 60, during isokinetic quadriceps contractions. To assure familiarization with the procedures the participant will have two practice submaximal trial repetitions set at the velocity of 60 and one practice trial. The test will consist of 5 repetitions at 60/s. There will be a 60 second interval between repetitions tested. During evaluation, the participants will be verbally instructed to move the lever of the dynamometer as fast and as powerfully as possible, trying to produce a maximum torque. Any complaints reported by the participant will be recorded in the comment section and, if necessary, the test will be stopped. Using the same seat set up, muscle performance will be evaluated during static concentric (isometric) quadriceps extension contractions. The lever arm will be positioned at 60 degrees of knee flexion, with the support cushion modified for the amputee and positioned at mid calf. The participant will have one practice submaximal trial contraction. The test will consist of three contractions for five seconds each. There will be a 60 second interval between each test. During evaluation, the participants will be verbally instructed to move the lever of the dynamometer as powerfully as possible, trying to produce a maximum torque. Any complaints reported by the participant will be recorded in the comment section and, if necessary, the test will be stopped.

At the 12 week visit, the intervention group participants will return the FES device. They will be followed up with one final visit 3 months after the FES device is returned.

At the end of the study, should the study find the FES intervention is beneficial, we will offer the control group the same intervention. It will be optional per participant request.

If a subject misses the last visit or is dropped from the study for a reason not related to the study and or beyond our control, we will ask to set up a follow up visit, face to face, or a phone interview to allow us to gather end result information and complete the data analysis.

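### Outside the socket-replacement rule, the plan assures no in-person assessment at a defined time, week 12 included, for participants who drop out, and a phone interview may take its place

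*Combined protocol and SAP*

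**What the plan says.** All the visit and retrieval rules stand in Study Design and Methods.

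- **Visits.** After baseline there are "four follow up visits at 4 weeks, 8 weeks, 12 weeks" and then "one final visit three months from the 12 week visit or from the discontinuation of the FES".
- **End of treatment.** "At the 12 week visit, the intervention group participants will return the FES device". Hypothesis 4 (under Background) expects that "FES training will show greater increases in velocity, step length, and percentage in stance time on the amputated limb after training". Hypotheses 1 to 3 name no time point, and no primary time point is defined.
- **General retrieval rule.** It begins "If a subject misses the last visit or is dropped from the study for a reason not related to the study", extends this to reasons outside the investigators' control, and then offers "a follow up visit, face to face, or a phone interview to allow us to gather end result information and complete the data analysis". The end result information is not defined.
- **Socket-replacement rule.** When a new socket is needed, the participant comes off FES, and "we will perform the above mentioned outcome measures and continue to follow them until the 3 month final follow up visit".
- **Measurement.** "Residual knee extension strength will be tested using a standardized Biodex protocol and a custom attachment". Limb volume comes from a hand-held laser scanner and gait from the GaitRite system. Pain and the PEQ are questionnaires that the participant completes. Pain is asked at all four follow-up visits; after baseline, the PEQ is asked only at 12 weeks and at the final visit.

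The Statistical Plan compares groups over time with a mixed-model repeated-measures ANOVA and falls back on the Friedman test if the data are not normal. It gives no rule for missing data and defines no analysis set.

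**The concern.** The device goes back at week 12, so that visit is the natural end-of-treatment assessment, and the final visit is off treatment by design. The general retrieval rule nevertheless names only one missed visit, the last. It limits retrieval by the reason for leaving, and it can be satisfied by a phone call.

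Two things are at stake. The first is avoidable loss: strength, volume and gait cannot be measured by phone, and a week-12 value that is missed need not be pursued at all. The second is selective loss. People who leave because of the study itself, for example because they do not tolerate the stimulation, are the group whose missing outcomes are most plausibly related to treatment, and they are the group for whom no retrieval is stated. Such losses would arise in the FES arm only, since controls receive no device.

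For pain there is a further, smaller issue. If the questionnaire is put to the participant over the phone, self-completed and staff-asked answers are mixed, and nothing requires the mode to be recorded.

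**Working it through.** The plan states no sample size, power, effect size, SD or drop-out rate, so there is no figure to reproduce. The check sets the rules side by side and adds simple timing arithmetic.

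**Step 1. Who is retrieved, and for what?**

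| Situation | Stated action | In-person outcome set at a defined time? |
|---|---|---|
| Off FES for socket replacement | Outcome measures, then follow-up to the final visit | Yes: at withdrawal and at the final visit; week 12 is not named |
| Misses the final visit | One visit or phone interview | No: undated, and phone is allowed |
| Dropped, reason unrelated to the study and/or beyond control | One visit or phone interview | No: undated, and phone is allowed |
| Dropped, study-related reason | None stated | No |
| Misses week 12 but stays in the study | None stated | No |

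**Step 2. When does the final visit fall?** It is timed at three months from week 12 or from stopping FES. Taking three months as 12 to 13 weeks (an assumption), final visit = stop week + 12 to 13:

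- FES to week 12: 12 + 12 = 24 to 12 + 13 = 25
- stop at week 2: weeks 14 to 15
- stop at week 6: weeks 18 to 19
- stop at week 10: weeks 22 to 23

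In every case the final visit is after week 12 and off treatment, so it cannot serve as the end-of-treatment value. A control has no FES to stop and is seen at weeks 24 to 25. An early stopper's final visit can therefore fall earlier after baseline than a control's: 12 − 2 = 10 weeks earlier for a stop at week 2. The text does not say whether the visits at weeks 4, 8 and 12 continue after an early stop.

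**Step 3. What can a phone interview supply?**

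| Hypothesis | Endpoint | Instrument | By phone? |
|---|---|---|---|
| 1 | Knee extension strength | Biodex | No |
| 2 | Residual limb volume | Laser scanner | No |
| 3 | Chronic and phantom pain | Questionnaire | Possible |
| 4 | Velocity, step length, stance time | GaitRite | No |

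The endpoints of three of the four hypotheses are out of reach. The PEQ could be asked by phone, but it is not the endpoint of a hypothesis.

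**Step 4. Does the analysis compensate?** A mixed model can use a participant's other visits when one is missing, but its validity then rests on why the value is missing, and the Statistical Plan does not address this. The Friedman test needs a value at every visit, so in that fallback one missed visit removes the participant from that outcome.

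**The case against.** The strongest defence is that the plan does more than a quick reading suggests, and much of it stands.

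- A reader might infer that there is only one catch-up rule, aimed solely at the last visit. The documents do not support this. The socket-replacement rule secures outcome measures at withdrawal and continued follow-up, and the general rule also covers participants dropped at any week.
- A reader might infer that drop-outs yield no week-12 value. The general rule gives no date, so a face-to-face contact could fall near week 12. Nothing bars rescheduling a missed visit, and someone who misses only the final visit may already have week-12 data. FES participants are also phoned every two weeks and must return the device. A week-12 value is not assured; it is not impossible.
- A reader might infer that phone and visit are treated as equivalent. The text lists the phone as an alternative without ranking it and does not call it equivalent. What the interview would ask is not stated.
- A reader might infer that week 12 decides the hypotheses, or that the later visit is least able to show an effect. No primary time point is named, the wording of Hypothesis 4 does not exclude the later visit, and no figure bears on the second claim.
- A reader might infer that an unblinded caller would bias the pain scores. A blinded assessor is described for baseline, and the plan does not say who makes retrieval calls. The mixing of modes is a real possibility; knowledge of the arm is conjecture.
- The limit on reasons is loosely worded. On its widest reading, a study-related reason beyond the investigators' control might be covered.

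These points narrow the claim without removing it. Beyond socket replacement, nothing commits the investigators to an in-person assessment at a set time, and the stated rule can be met in full by a phone call.

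**Conclusion.** The concern holds in this limited form. Outside socket replacement, the plan assures no in-person outcome assessment at a defined time, including week 12, for participants who drop out. It states no retrieval for study-related drop-outs or for a missed week-12 visit. The phone interview that it allows cannot supply the endpoints of Hypotheses 1, 2 and 4.

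The size can be given only as coverage: three of four hypotheses get nothing from a phone contact. Neither the number of participants affected nor the loss of power can be calculated, because no sample size or drop-out rate is stated. The conclusion rests on treating week 12 as the end of treatment, which the return of the device supports, and on reading the limit on reasons as excluding at least some study-related drop-outs. The 12-to-13-week reading of three months affects only the illustrative visit dates.

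This is a cheap improvement, not a flaw that invalidates the design. The socket-replacement rule shows that the investigators already accept assessing and following people after FES stops.

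**What to change.** In Study Design and Methods, replace the general retrieval sentence with a rule along these lines:

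1. Every randomised participant who misses the 12-week or final visit, who stops FES, or who is dropped for any reason, and who has not withdrawn consent for follow-up, is asked to attend in person for the full outcome set. Attendance is as close as possible to the scheduled week-12 and final dates, and the actual date is recorded.
2. If attendance is refused, the pain questionnaire and PEQ are sent for self-completion.
3. A phone interview is the last resort, uses those same items only, and its mode is recorded.
4. The pain analysis is repeated without phone-collected values.

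The date of the final visit must be reconciled with the present wording, which allows it to run from the discontinuation of FES, so that it is clear which date applies after an early stop.

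The cost is protocol wording, a few rescheduled visits using existing procedures, and one sensitivity analysis. The downside is that some visits will fall outside the planned date, which is why the actual date should be recorded.
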